7.1.2. Exclusion Criteria

A patient will not be eligible for participation in this study if *any* of the following criteria apply.

- 1. Treatment with any of the following:
 - a. EGFR TKIs (erlotinib, gefitinib, afatinib, osimertinib) within 9 days of the first dose of study drug; other approved EGFR TKIs within 5 half-lives of the first dose of study drug

- b. Investigational agents within 28 days, or 5 half-lives, whichever is longer, of the first dose of study drug; antibody based therapy within 6 weeks of the first dose of study drug
- c. *Part 1:* More than 2 prior lines of cytotoxic chemotherapy for advanced NSCLC
- d. Part 2: Previous treatment with osimertinib or other T790M active EGFR TKI
- e. Part 2: Any prior cytotoxic chemotherapy for advanced NSCLC
- 2. Major surgery within 14 days of the first screening visit
- 3. Blood transfusions or hematopoietic growth factor therapy within 14 days prior of first screening visit
- 4. Prior radiotherapy treatment to > 25% of the bone marrow or radiotherapy with a wide field of radiation within 28 days of the first dose of study drug
- 5. Patients receiving medications, herbal supplements, or foods known to be potent inhibitors of CYP3A4 or orally administered sensitive substrates of CYP3A4 within 14 days prior to first dose of study drug, including but not limited to the following:
 - a. **Inhibitors**, for example: clarithromycin, diltiazem, erythromycin, grapefruit juice, itraconazole, ketoconazole, nefazodone, ritonavir, telithromycin, and verapamil
 - b. **Substrates**, for example: astemizole, cisapride, cyclosporine, dihydroergotamine, ergotamine, everolimus, pimozide, quinidine, sirolimus, and tacrolimus
- 6. Patients receiving medications, herbal supplements, or foods known to be potent inducers of CYP3A4 within 21 days prior to the first dose of study drug, including but not limited to the following:
 - a. **Inducers**, for example: carbamazepine, *Hypericum perforatum* (St. John's wort), phenobarbital, phenytoin, rifampin
- 7. Patients receiving medications, herbal supplements, or foods known to be potent inhibitors of BCRP within 14 days prior to first dose of study drug, including but not limited to the following:
 - a. **Inhibitors**, for example: sulfasalazine, curcumin, turmeric supplements, cyclosporine, eltrombopag
- 8. *Part 1:* Patients receiving medications that raise gastric pH within 7 days prior to first dose of study drug such as proton pump inhibitors (eg, omeprazole, pantoprazole, lansoprazole, esomeprazole, rabeprazole, dexlansoprazole), H2 blockers (eg, nizatidine,

- famotidine, cimetidine, ranitidine), and antacids (eg, sodium bicarbonate, calcium carbonate, aluminum-based antacids, magnesium compounds, alginic acid).
- 9. Any unresolved toxicities from prior surgeries or therapy of > Grade 1 (CTCAE, Version 4.03) at the time of starting study drug with the exception of alopecia (any grade) and platinum therapy-related peripheral neuropathy (> Grade 2)
- 10. Known active uncontrolled or symptomatic central nervous system (CNS) metastases, carcinomatous meningitis, or leptomeningeal disease as indicated by clinical symptoms, cerebral edema, and/or progressive growth. Patients with a history of CNS metastases or cord compression are eligible if they are currently asymptomatic and clinically stable off anticonvulsants and steroids for at least 28 days prior to first dose of G1T38.
- 11. Any evidence of severe or uncontrolled systemic diseases, including uncontrolled hypertension and active bleeding diatheses, which in the investigator's opinion makes it undesirable for the patient to participate in the study or which would jeopardize compliance with the protocol
- 12. Known chronic, active infection including but not limited to hepatitis B virus, hepatitis C virus, tuberculosis, and human immunodeficiency virus (HIV); screening for chronic conditions is not required
- 13. Any of the following cardiac criteria:
 - a. Mean resting corrected QT interval (QTc) > 470 msec obtained from 3 electrocardiograms (ECGs), using the screening clinic ECG machine derived QTc value
 - b. Any clinically important abnormalities in rhythm, conduction, or morphology or resting ECG, eg, complete left bundle branch block, third degree heart block, second degree heart block, PR interval > 250 msec
 - c. Any factors that increase the risk of QTc prolongation (see Appendix 3 for list of drugs) or risk of arrhythmic events such as heart failure, hypokalemia, congenital long QT syndrome, family history of long QT syndrome or unexplained sudden death under 40 years of age in first degree relatives, or any concomitant medication known to prolong the QT interval
 - d. Uncontrolled ischemic heart disease or uncontrolled symptomatic congestive heart failure (Class III or IV as defined by the New York Heart Association [NYHA] functional classification system)
 - e. Known history of stroke, cerebrovascular accident, or myocardial infarction within 6 months prior to first dose of study drug
- 14. Past medical history of interstitial lung disease (ILD), drug-induced ILD, radiation pneumonitis which required steroid treatment, or any evidence of clinically active interstitial lung disease

- 15. Refractory nausea and vomiting, chronic gastrointestinal disease, gastrointestinal ulcer, gastrointestinal bleeding, inability to swallow the formulated product, or previous significant bowel resection that would preclude adequate absorption of study drug
- 16. History of other malignancies, except for the following: (1) adequately treated basal or squamous cell carcinoma of the skin; (2) curatively treated a) in situ carcinoma of the uterine cervix, b) prostate cancer, or c) superficial bladder cancer; or (3) other curatively treated solid tumor with no evidence of disease for ≥ 3 years
- 17. History of hypersensitivity to active or inactive excipients of study drug or drugs with a similar chemical structure or class to study drug
- 18. Women who are pregnant or breastfeeding
- 19. Psychiatric illness/social situations that would limit study compliance
- 20. Legal incapacity or limited legal capacity
- 21. Judgement by the investigator that the patient should not participate in the study if the patient is unlikely to comply with study procedures, restrictions, and requirements
- 22. Prior hematopoietic stem cell or bone marrow transplantation

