- o *Part 1 only*: More than 2 prior lines of cytotoxic chemotherapy for advanced NSCLC
- o *Part 2 only*: Any prior cytotoxic chemotherapy for advanced NSCLC
 - Part 2 only: Previous treatment with osimertinib or other T790M active EGFR TKI
- Blood transfusions or hematopoietic growth factor therapy within 14 days of first screening visit
- o Prior radiotherapy treatment to > 25% of the bone marrow or radiotherapy with a wide field of radiation within 28 days of the

first dose of study drug

- Patients receiving medications, herbal supplements, or foods known to be potent inhibitors of cytochrome P450 (CYP)3A4 or orally administered sensitive substrates of CYP3A4 within 14 days prior to first dose of study drug (see Sections 8.5.1 and 8.5.2)
- Patients receiving medications, herbal supplements, or foods known to be potent inducers of CYP3A4 within 21 days prior to first dose of study drug (see Section 8.5.2)
- Patients receiving medications, herbal supplements, or foods known to be potent inhibitors of BCRP within 14 days prior to first dose of study drug (see Section 8.5.2)
- Part 1 only: Patients receiving medications that raise gastric pH within 7 days prior to first dose of study drug (see Section 8.5.5).
- Any unresolved toxicities from prior surgeries or therapy
 Grade 1 (Common Terminology Criteria for Adverse Events [CTCAE] Version 4.03) at the time of starting study drug with the exception of alopecia (any grade) and platinum therapyrelated peripheral neuropathy (> Grade 2)
- Known active uncontrolled or symptomatic central nervous system (CNS) metastases, carcinomatous meningitis, or leptomeningeal disease as indicated by clinical symptoms, cerebral edema, and/or progressive growth. Patients with a history of CNS metastases or cord compression are eligible if they are currently asymptomatic and clinically stable off anticonvulsants and steroids for at least 28 days prior to first dose of G1T38.
- Any evidence of severe or uncontrolled systemic diseases, including uncontrolled hypertension and active bleeding diatheses, which in the investigator's opinion makes it undesirable for the patient to participate in the study or which would jeopardize compliance with the protocol
- Known chronic, active infection
- Cardiac criteria as outlined in Section 7.1.2

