7.1.1. Inclusion Criteria

Patient eligibility shall be reviewed and documented by an appropriately qualified member of the investigator's study team before patients are included in the study. Patients must meet all of the following inclusion criteria to be eligible for enrollment into the study:

- 1. Provision of signed and dated written informed consent prior to any study specific procedures, sampling, and analysis
- 2. Women or men, 18 years or older
- 3. Histologic or cytologic confirmed diagnosis of NSCLC
- 4. Stage IV NSCLC
- 5. Documented EGFR mutation (at any time since the initial diagnosis of NSCLC) known to be associated with EGFR TKI sensitivity (including G719X, exon 19 deletion, L858R, L861Q). Patients in Part 1 that are EGFR TKI treatment naive will be enrolled based on a locally available EGFR mutation test result that has been FDA-approved and performed in a Clinical Laboratory Improvement Amendments (CLIA)-certified laboratory (US sites) or based on a locally available EGFR mutation test result that has been performed in an accredited laboratory (sites outside of the US).
 - a. *Part 2 Only*: Tumor EGFR T790M mutation-positive status after documented disease progression on first-line treatment with a first or second generation EGFR TKI. Patients will be enrolled based on a locally available T790M mutation test result (tumor biopsy or cell-free DNA [cfDNA]) that has been FDA-approved (eg, cobas[®] EGFR Mutation Test v2, FoundationOne CDxTM) and performed in a CLIA-certified laboratory (US sites) or a locally available T790M mutation test result (tumor biopsy or cfDNA) that has been performed in an accredited laboratory (sites outside of the US). Testing for the presence of the T790M mutation in plasma specimens (cfDNA) is recommended only in patients for whom a tumor biopsy cannot be obtained.
- 6. Eastern Cooperative Oncology Group (ECOG) performance status of 0 or 1, with no deterioration over the previous 2 weeks and a minimum life expectancy of 12 weeks

- 7. Evaluable disease (Part 1 only) or measurable disease as defined in Response Evaluation Criteria in Solid Tumors (RECIST), Version 1.1, as determined by the investigator

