10.6.1.1. Definition of Adverse Event

An AE is defined as any untoward medical occurrence in a patient administered a medicinal product that does not necessarily have a causal relationship with this treatment. An AE can, therefore, be any unfavorable and unintended sign (including an abnormal laboratory finding), symptom, or disease temporally associated with the use of a medicinal (investigational) product, whether or not related to the study (investigational) product.

Adverse events include the following:

- All suspected study drug-related adverse events
- All reactions from medication overdose, abuse, withdrawal, sensitivity, or toxicity
- Apparently unrelated illnesses, including the worsening of a pre-existing illness (see pre-existing conditions below)
- Injury or accidents (Note that if a medical condition is known to have caused the injury or accident [eg, a fall secondary to dizziness], the medical condition [dizziness] and the accident [fall] should be reported as 2 separate AEs). The outcome of the accident (eg, hip fracture secondary to the fall) should be recorded under comments.
- Abnormalities in physiological testing or physical examination (findings that require clinical intervention or further investigation beyond ordering a repeat [confirmatory] test)
- Laboratory abnormalities that are clinically significant and require clinical intervention or further investigation (beyond ordering a repeat [confirmatory] test) unless they are associated with an already reported clinical event. Laboratory abnormalities associated with a clinical event (eg, elevated liver enzymes in a patient with jaundice) should be described under comments on the report of the clinical event rather than listed as a separate AE.

An AE does not include:

- Medical or surgical procedures (eg, surgery, endoscopy, tooth extraction, transfusion); the condition that leads to the procedure may be an AE
- Pre-existing diseases or conditions present or detected at the start of the study that do not worsen
- Situations where an untoward medical occurrence has not occurred (eg, hospitalization for elective surgery, social, and/or convenience admissions)
- Overdose of either study drug or concomitant medication without any signs or symptoms
- Progression of the malignancy under study, including signs and symptoms progression

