10.6.1.4. Assessment of the Causal Relationship of Adverse Events to Study Drug

The investigator will assess causal relationship between study drug and each Adverse Event and classify each AE as either related or unrelated. In determining if an AE is study drug related, the Investigator shall take into account the following question: "Is there a reasonable possibility that the event may have been caused by the study drug?" Investigators shall use their knowledge of the patient, the circumstances surrounding the event, and an evaluation of any potential alternative causes to determine whether or not an adverse event is considered to be related or unrelated to study drug. The following guidance shall be taken into consideration when determining causality:

- Temporal relationship of event onset to the initiation of study drug
- Course of the event, considering especially the effects of dose reduction, discontinuation of study drug, or reintroduction of study drug (as applicable)
- Known association of the event with the study drug or with similar treatments
- Known association of the event with the disease under study
- Presence of risk factors in the patient or use of concomitant medications known to increase the occurrence of the event
- Presence of non-treatment-related factors that are known to be associated with the occurrence of the event

The following terms for assessment of the causality to study drug or study procedures are to be used:

- Unrelated: There is not a temporal relationship to study drug administration (eg, too early, too late, or study drug not taken), or there is a reasonable causal relationship between another drug, concurrent disease, or circumstance and the AE.
- **Related**: There is a reasonable causal relationship between the study drug and the AE. The event responds to withdrawal of study drug, and recurs with re-challenge, when clinically feasible.

For patients receiving combination therapy, causality will be assessed individually for each study drug.

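### Exclusion 9 excepts platinum neuropathy above Grade 2 from the toxicity bar; read literally, this admits Grades 3-4 and excludes Grade 2

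*Protocol*

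**What the plan says.** Exclusion 9 in Protocol Section 7.1.2 excludes patients whose toxicities from earlier surgery or therapy remain above CTCAE Grade 1 when study drug starts, "with the exception of alopecia (any grade) and platinum therapy-related peripheral neuropathy (> Grade 2"). The synopsis (Key Criteria for Exclusion) carries the same exception: "platinum therapyrelated peripheral neuropathy (> Grade 2").

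The exception matters in Part 1, where exclusion 1c removes only patients with "More than 2 prior lines of cytotoxic chemotherapy for advanced NSCLC", so up to two such lines are permitted. Part 2 barred any earlier cytotoxic chemotherapy for advanced disease, and SAP Section 1 records that Part 2 is not being run.

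Three other criteria bear on the same patients without naming a neuropathy grade:

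- Inclusion 6 requires ECOG "performance status of 0 or 1, with no deterioration over the previous 2 weeks".
- Exclusion 11 covers "Any evidence of severe or uncontrolled systemic diseases" that the investigator considers unsuitable for the study.
- Exclusion 21 rests on "Judgement by the investigator that the patient should not participate in the study" because of likely non-compliance.

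The list of changes from the protocol in SAP Section 7 does not mention exclusion 9.

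**The concern.** The two exceptions sit side by side and are built alike. The bracket after alopecia states which grades are let through. On the same construction, the bracket after neuropathy lets through everything above Grade 2. Grade 2 is above the general bar and outside the exception, so it stays excluded. A rule that bars moderate neuropathy and accepts severe neuropathy has no evident rationale, so the sign probably points the wrong way for the sentence it is in.

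Two things are at stake. First, patients with severe neuropathy could enter when they were probably meant to be kept out. Second, any worsening on study becomes harder to attribute. Part 1's primary objectives are dose-limiting toxicities, the recommended Phase 2 dose and safety. A dose-limiting toxicity must be drug-related and includes nonhematologic toxicity of Grade 3 or higher (Protocol Section 6.1.1.2). The causality guidance in Section 10.6.1.4 asks the investigator to weigh "Presence of non-treatment-related factors that are known to be associated with the occurrence of the event", and severe neuropathy at entry is such a factor.

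**Working it through.** No sample size, power or error rate is involved, and the plan gives no figure to reproduce. The check is to apply the rule grade by grade.

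**Inputs**

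- General bar: excluded if the grade is above 1, unless excepted (exclusion 9).
- Exception as it reads in both copies: platinum-related neuropathy, > Grade 2 (exclusion 9 and synopsis).
- Reference rule, taken as the probable intent (an assumption): neuropathy up to and including Grade 2 is tolerated.

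**Rule:** a patient is excluded if grade > 1 and the grade is not excepted. E = eligible, X = excluded.

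| Reading of the neuropathy bracket | Gr 1 | Gr 2 | Gr 3 | Gr 4 | Grades differing from reference |
|---|---|---|---|---|---|
| Reference: Grade 2 or lower allowed | E | E | X | X | - |
| (1) > 2, as the grades excepted (literal) | E | X | E | E | 2, 3, 4: 3 of 4 |
| (2) ≥ 2, as the grades excepted | E | E | E | E | 3, 4: 2 of 4 |
| (3) ≥ 2, as an exclusion cut-off | E | X | X | X | 2: 1 of 4 |
| (4) > 2, as an exclusion cut-off | E | E | X | X | 0 of 4 |
| (5) ≤ 2, as the grades excepted | E | E | X | X | 0 of 4 |

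Grade 1 is eligible on every reading. Grades 2, 3 and 4 change status between readings, so eligibility is unsettled at 3 of 4 grades. With the sign as it appears, the two available readings, (1) and (4), give opposite answers at all three.

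**Reliability of the sign.** Readings (2), (3) and (5) are included because comparison signs in the extracted text are not fully dependable. The synopsis copy of this criterion has lost the sign before Grade 1, and the AST limit appears as ≤ in the synopsis but < in Section 7.1.1. Both copies of the neuropathy bracket read >. If the printed sign is ≥, the literal reading still has no upper limit. If it is ≤, the point falls.

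**What else could supply a limit.** ECOG 0-1, exclusion 11 and exclusion 21 narrow the group, but none is a neuropathy grade limit, and the two exclusions turn on individual judgement. No other criterion sets one.

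**What is already captured.** Screening includes a neurological examination, with significant findings recorded as medical history (Section 10.6.4). The adverse event definition includes "Apparently unrelated illnesses, including the worsening of a pre-existing illness". Baseline neuropathy and its worsening should therefore be visible in the data.

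**Numbers exposed.** Part 1 may enroll up to 36 patients. The documents give no rate of platinum exposure or neuropathy, so the count lies somewhere from 0 to 36 and cannot be narrowed.

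**The case against.** The strongest case on the other side is that sites would not read the bracket literally. It sits in a list of exclusion criteria, and the first sign in the sentence, above Grade 1, is an exclusion threshold. Taking the second as a raised threshold makes both signs do the same work and yields the sensible rule, reading (4), with no mismatch. The literal result is clinically absurd. Agreement between the two copies is also weaker support than it looks: ALT reads < in both places while the companion AST limit does not agree, so matching copies do not prove a sign was read correctly. Protocol Section 15.1 requires monitors to verify eligibility in full. Finally, Part 2 was dropped and the SAP plans only a final Part 1 analysis once all patients are off treatment, so the study appears to be winding down and an amendment may come too late to matter.

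Much of this stands. The cut-off reading is probably the intent and may be actual practice, the harm is hypothetical, and the remedy may be partly moot. It does not remove the defect. The bracket follows words of exception, and its neighbour names permitted grades, so the text does not say what was probably meant. Monitoring checks patients against the same ambiguous criterion and cannot supply the missing ceiling. The visible extraction faults are lost signs or lost bars; none shows a reversed direction.

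**Conclusion.** The concern holds and is minor. As the text stands, the exception to exclusion 9 read literally admits platinum neuropathy of Grades 3-4 and excludes Grade 2, and nothing else in either document sets a grade limit. The mismatch with a rule tolerating up to Grade 2 is 3 of 4 grades on the literal reading and 0 of 4 if the bracket is taken as an exclusion cut-off. These are counts of grades under different readings; they do not measure an effect on results.

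The conclusion rests on the printed sign being > (or ≥, which also leaves the literal reading open-ended) and on Grade 2 or lower being the intended ceiling. The practical effect is confined to Part 1 patients with earlier platinum therapy. No endpoint, dose-limiting toxicity rule or planned estimate changes. What remains is avoidable entry of patients with severe neuropathy and harder attribution of any worsening.

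**What to change.** Confirm the sign in the printed protocol. If it is not already ≤, change the bracket in exclusion 9 and in the synopsis to platinum therapy-related peripheral neuropathy of Grade 2 or lower, with the medical team confirming that ceiling. Apply it going forward only. This reduces the attribution problem but does not remove it, because Grade 2 would still be admitted.

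Patients already enrolled should not be classed as deviations against the new ceiling, since Section 14.5 judges deviations against the protocol as it stood. A short listing of any with baseline platinum neuropathy above Grade 1, with a note at the pre-lock Classification Meeting (SAP Section 5.2.2) of which reading was applied, is enough. If Part 1 enrollment has closed, which the documents do not say, only this listing remains. It is the lesser part of the fix. The planned medical history listing (SAP Section 5.2.5) does not name neuropathy grade, so the grade may have to come from source records.

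The cost is one line in two places, plus submission to the ethics committees under Section 14.6, which applies even to nonsubstantial amendments, and one short listing for a meeting already planned.
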